### **Patients**

From January 2019, consecutive patients with suspected UNE will be prospectively recruited in a single referral centre (Institute of Clinical Neurophysiology, University Medical Center Ljubljana, Slovenia). Inclusion criteria will be: (1) sensory loss in the 5th finger; (2) weakness of 2nd and 5th finger abduction; and (3) UNE confirmed and precisely localized by short-segment nerve conduction studies (NCSs) and US. Exclusion criteria will be: (1) previous elbow fracture or surgery; (2) sensory loss outside of the ulnar innervation area; (3) an ulnar nerve conduction block of  $> 20\%$  in the elbow segment; (4) C8 radiculopathy, lower brachial plexopathy, or ulnar neuropathy at the wrist; (5) polyneuropathy or multiple mononeuropathy; (6) spinal cord anterior horn cell disorders (e.g., monomelic amyotrophy, amyotrophic lateral sclerosis).

The trial protocol will conform to CONSORT guidelines. Written informed consent will be obtained from all patients before their inclusion into the study. The trial was approved by the National Ethics Committee of Slovenia (Nr. 0120-497/2018/5) and was registered on the 27th of August 2018 at ClinicalTrials.gov (NCT03651609).

### **History and Clinical Neurologic Examination**

The first examiner will collect demographic and clinical data using a standard questionnaire for assessment of UNE severity (UNEQ). The UNEQ considers the patient's numbness and tingling of the last two fingers, elbow pain, and changes in these symptoms with elbow

position. It also evaluates hand weakness. Questionnaire items are graded as: 1 – absent, 2 – mild, 3 – moderate, 4 – severe, or 5 – very severe. The final UNEQ score is calculated as the mean of the nine items. Patients will also report whether UNE symptoms: 1 – improved, 2 – remained unchanged, or 3 – worsened. The first examiner will also perform a focused neurological examination and graded: (1) muscle wasting of the first dorsal interosseous (FDI) and abductor digiti minimi (ADM) muscles (0 – absent, 1 – mild, 2 – moderate or 3 – severe); (2) muscle strength of FDI, ADM, and four indicator forearm muscles using the modified MRC scale; and (3) light touch and pin-prick sensation on the tip of the 5th and 2nd finger, ulnar sides of the 4th finger, palm, and hand dorsum as well as the forearm (0 – normal, 1 – moderately reduced, 2 – severely reduced or 3 – absent). For statistical analyses, the modified MRC scale will be transformed as follows: MRC grade 0 = 0, 1 = 1, 2 = 2, 3 = 3, 4 = 4, 4 = 5, 4+ = 6, and 5 = 7. Clinical UNE severity was graded: (1) *Mild* UNE – reduced sensation in the ulnar-innervated areas; (2) *Moderate* UNE – + ulnar hand muscle weakness, and (3) *Severe* UNE – + at least moderate ulnar hand muscle atrophy.

### **Electrodiagnostic Examination (EDx)**

The second examiner (clinical neurophysiologist > 25 years) will also perform motor and sensory NCSs of the ulnar and median nerve in the affected arms using a standard EMG system (Nicolet Synergy, Natus Medical Incorporated, San Carlos, USA). Compound muscle action potentials (CMAPs) will be recorded from the ADM and abductor pollicis brevis (APB) muscles using disposable adhesive surface electrodes. With the elbow flexed at 90°, the ulnar nerve will be stimulated at the wrist, ME, 2 and 4 cm distal (D2, D4), and 2 and 4 cm proximal (P2, P4) to ME (i.e., short-segment NCSs). The median nerve will be stimulated at the wrist and the elbow. Ulnar and median antidromic sensory nerve action potentials

(SNAPs) will be recorded from the 5th and 2nd fingers on stimulation 14 cm proximally at the wrist.

Using short-segment NCSs, UNE will be diagnosed and localized to a 2-cm ulnar nerve segment with either motor nerve conduction velocity (MNCV)  $< 31$  m/s (the lower reference limit) or a CMAP amplitude drop  $> 12\%$  (the upper reference limit) (Fig. 1).

### **Ultrasonography (US)**

The third examiner (US technician  $> 10$  years) will measure the ulnar and median nerve CSAs in the affected arm using a standard US device (ProSound Alpha 7, Hitachi Aloka Medical, Ltd., Tokyo, Japan) with a 13 MHz linear array transducer (UST-5412, Hitachi Aloka Medical, Ltd., Tokyo, Japan). During the US examination, the probe will be positioned perpendicular to the nerve, and minimal pressure will be applied. A trace method will be used for CSA measurements, and the nerve hyperechoic rim will be excluded. Ulnar nerve CSA will be measured at the wrist, D4, D2, ME, P2, and P4. In addition, ulnar nerve CSA will be measured at the site of maximal CSA (CSAmax) and minimal CSA (CSAmin). Median nerve CSA will be measured at the wrist and 10 cm proximally.

Using the US, UNE will be diagnosed and localized as follows: (1) if a clear constriction (i.e., a focal narrowing of at least  $2 \text{ mm}^2$  relative to the nerve size proximally and distally) will be seen distal to the ME then the case will be classified as CTE; (2) if a focal enlargement  $> 10 \text{ mm}^2$  at or proximal to the ME will be seen then the case will be classified as RCC; (3) in cases where CSAmax ( $> 10 \text{ mm}^2$ ) will be found distal to the ME, but nerve constriction will not be seen, then the entrapment site will be taken to be located just distal to the nerve enlargement and the case will be classified as CTE. In arms with discordant EDx and US localisation, US will be given preference.

## **Randomization and Masking**

The study will have a parallel trial design with a 1:1 allocation ratio, and a trial CONSORT diagram will be drawn. CTE and RCC patients will be separately randomized by one of the authors (SP), throwing dice as follows: (1) even number – surgical release, and (2) odd number – conservative treatment. In patients with bilateral UNE, the more affected arm will be randomized. Patients randomized to the surgical arm will be referred to a plastic surgeon. All included CTE and RCC patients (also those randomized to surgical release) will be given illustrated instructions showing arm positions they should avoid to prevent further ulnar nerve damage due to external compression.

The examiners will be blinded to the patient's study arm and the findings of other parts of the patient evaluation. During follow-up, examiners performing EDx and US examinations will be able to see a post-operative scar, but will be unaware of the patient group (i.e., CTE vs. RCC). Patients will not be blinded to treatment.

## **Treatment**

The surgeon will perform division of the HUA 2-3 cm distal to ME in CTE and RCC patients.

To prevent potential harm due to the delay of surgery, CTE patients randomized to a conservative arm will also be seen at 3 and 6 months. In case of clear clinical progression, they will be referred for immediate surgery. After 12 months of follow-up, these patients will be advised to proceed to surgery. CTE patients randomized to a surgery arm will be seen at 6 months for calculation of the sample size.

## **Sample Size Calculation**

The required number of patients in the treatment arms will be determined after the first 20 patients in both CTE treatment arms have completed 6 months of follow-up. We will calculate the proportions of patients perceiving symptom improvement in both treatment arms and a standardized difference. For 80% power, the necessary sample size will be determined using a nomogram for calculating sample size.

### **Primary and Secondary Outcome Measures**

At 12-month follow-up (after surgery or the start of conservative treatment), all patients will be evaluated using the same protocol as during the initial evaluation. The primary outcome measure of the study will be the change in UNEQ score from baseline at inclusion of patients into the study and at 12-month follow-up.

The secondary outcome measures will be changes in: (1) clinical UNE severity; (2) atrophy of the ADM and FDI muscles; (3) strength of the ADM and FDI muscles using the modified MRC scale; (4) light touch sensation on the tip of the 5th finger; (5) ulnar MNCVmin across the elbow; (6) the amplitude of the ulnar CMAP on stimulation at D4; (7) the amplitude of the ulnar SNAP; (8) ulnar nerve CSAmax in the elbow segment; (9) ulnar nerve CSAmin in the elbow segment.

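### Does timing the 12-month visit from surgery or the start of conservative treatment, while measuring UNEQ change from inclusion, distort the comparison of arms?

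*Combined protocol and SAP*

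**What the plan says.** Under Primary and Secondary Outcome Measures, the visit is timed by treatment: "At 12-month follow-up (after surgery or the start of conservative treatment), all patients will be evaluated". The next sentence defines the primary outcome as the UNEQ change "from baseline at inclusion of patients into the study and at 12-month follow-up". Baseline is thus inclusion for everyone, while the clock for the visit starts at surgery in one arm and at conservative treatment in the other.

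Under Randomization and Masking, the only statement about the route to surgery is "Patients randomized to the surgical arm will be referred to a plastic surgeon". No waiting time, upper limit or repeat pre-operative baseline is given. The same section says "CTE and RCC patients will be separately randomized" and describes the positioning advice that both arms receive: "All included CTE and RCC patients (also those randomized to surgical release) will be given illustrated instructions".

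Under Treatment, conservative-arm CTE patients "will also be seen at 3 and 6 months", and the stated reason is "To prevent potential harm due to the delay of surgery". For those who worsen, the text says "In case of clear clinical progression, they will be referred for immediate surgery". No early-switch rule is stated for RCC.

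The Statistics section plans an unadjusted two-group test. Its counterpart under Changes to the protocol records that Mann-Whitney was used. Neither has a term for elapsed time.

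**The concern.** A change score covers whatever happens between its two measurements. If operated patients waited some months, their score covers a longer period than the conservative score, and any drift in symptoms during the wait is credited to the arm. Randomisation does not remove this, because the timing rule itself makes the interval depend on the arm. The Treatment section also treats delay as potentially harmful in CTE, so the assumption that nothing happens while waiting is not obviously safe.

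Early switchers raise a second question. A conservative-arm CTE patient operated on after the 3- or 6-month visit has both a conservative start and a surgery date, so either could be taken as the origin. If the waits were long or the switchers many, the primary comparison could be shifted by an amount that a reader of this document cannot check.

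**Working it through.** The plan states no interval, so there is no figure of its own to reproduce. The check asks how far the intervals could differ and what that would do to the test.

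**1. Elapsed time.** Let w be the wait from inclusion to surgery (assumed), and take conservative treatment to start at inclusion. That is reasonable, because the only content described is the positioning advice. The surgical interval is 12 + w and the conservative interval is 12.

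| w (months) | Surgical interval | Ratio to 12 |
|---|---|---|
| 0 | 12 | 1.00 |
| 1 | 13 | 1.08 |
| 2 | 14 | 1.17 |
| 3 | 15 | 1.25 |
| 6 | 18 | 1.50 |

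**2. Early switchers**, operated on at once after the visit at month s:
- Origin at conservative start: assessed at 12 months, which is 12 − 3 = 9 or 12 − 6 = 6 months after surgery.
- Origin at surgery: assessed at 3 + 12 = 15 or 6 + 12 = 18 months after inclusion.

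The two readings differ by 3 or 6 months, for these patients only. Their number is not given.

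**3. Size of the CTE comparison.** Under Changes to the protocol, 8 CTE patients are 13% of the total. The totals that fit are 60 (13.3%) to 63 (12.7%), or 64 if 12.5% is rounded up. That is about 31 per arm if the arms are equal. RCC arm sizes are not given, so no RCC figure is offered.

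**4. Effect on the test.** Let r be the UNEQ drift in SD per month (assumed 0.02 to 0.05), with no surgical effect and the drift carried in full to the final visit. The spurious shift is d = r × w. For a two-sided 5% t-test with 31 per arm (60 df), the noncentrality is d × √(31/2) = 3.937d. The Mann-Whitney column is a simulation with 40,000 replicates and normal data; a dash means not simulated.

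| w | r | d | 3.937d | t-test rate | Mann-Whitney rate |
|---|---|---|---|---|---|
| 0 | – | 0 | 0 | 5.0% | 4.7% |
| 1 | 0.02 | 0.02 | 0.079 | 5.1% | 4.9% |
| 1 | 0.05 | 0.05 | 0.197 | 5.4% | 5.2% |
| 2 | 0.02 | 0.04 | 0.157 | 5.3% | – |
| 2 | 0.05 | 0.10 | 0.394 | 6.7% | – |
| 3 | 0.02 | 0.06 | 0.236 | 5.6% | 5.5% |
| 3 | 0.05 | 0.15 | 0.591 | 9.0% | 8.7% |
| 6 | 0.02 | 0.12 | 0.472 | 7.5% | 7.0% |
| 6 | 0.05 | 0.30 | 1.181 | 21.3% | 20.3% |

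The t-test rate reaches 10% at d = 0.168. That needs a mean wait of 0.168/0.05 = 3.4 months at the faster drift, or 0.168/0.02 = 8.4 months at the slower.

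**5. The alternative clock.** Counting 12 months from randomisation in both arms would equalise the interval from baseline, but it leaves operated patients only 12 − w months of recovery (9 months if w = 3). One imbalance would replace another.

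**The case for a change.** The case for acting is a fair one. The two origins stand in adjacent sentences, nothing elsewhere bounds the wait, and prompt surgery is a hope that no section supports. The switcher ambiguity exists even if surgical-arm waits were nil. The document was revised after results were known, since it reports outcome counts, so the intervals could have been added at little cost. A sensitivity analysis could also subtract an assumed monthly drift for each month beyond 12 and show where the conclusion changes.

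The factual part stands: the wait, the visit intervals and the switcher origin are not written down here. It does not amount to a fault in the design or the analysis. A protocol and SAP with a short change log is not where realised intervals and switcher counts normally appear. The plan commits to CONSORT guidelines and a flow diagram, and the trial report may well give them.

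The sensitivity analysis adds little. The drift would still be assumed. Estimating it from non-operated conservative patients leaves out those who progressed, which makes the drift look milder. Pre-operative change need not carry through to the 12-month score if surgery works. A trigger of about 1 month's difference between arms would start a re-analysis where the rates in the table barely move. Statisticians could reasonably differ on whether to run it.

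**Conclusion.** No change to the plan follows. The two origins do different jobs and do not contradict each other: a change score needs a measurement before treatment, and the visit is placed to give each arm the same time after its treatment began. Timing from randomisation would be a trade-off, not a correction.

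The switcher origin is a gap that analysts fill sensibly. Grouping by randomised arm keeps the start of conservative treatment as the origin, and this fits the Treatment section, which describes a 12-month follow-up for that arm. The document does not state this reading, but it is the natural one.

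No bias is shown in either direction. With waits of about a month the effect on the error rate is negligible. The figures near 20% need a 6-month wait and the faster drift together. Both are assumptions, as are linear drift, full carry-through, equal arms of 31 and normal data for the simulation. Anyone writing or reading the trial report should look for time from inclusion to surgery and to the final visit by arm, within CTE and RCC, and for the number of early switchers. That is ordinary reporting.

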### **Statistics**

All data will be transferred into a Microsoft Excel (Microsoft Corp., Redmond, Washington, USA) spreadsheet and analysed using Statistics Kingdom, an internet-based statistical package. Distribution of numerical variables will be established by the Shapiro-Wilk test. In case of non-normal distribution, non-parametric descriptive statistics (i.e., median (25th–75th percentile)) and a non-parametric comparison test (Mann-Whitney U) will be used. In case of normal distribution, parametric descriptive statistics (i.e., mean (SD – standard deviation))

and a parametric comparison test (a two-sample t-test) will be used. Categorical variables will be presented as frequencies and percentages. A two-sample Z-test will be used to calculate the difference between the two proportions. All tests will be performed at a significance level of  $\alpha = 0.05$  (two-sided).

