## **Sample Size Calculation**

The sample size was calculated using the initial primary outcome measure because we do not know the minimal clinically important difference for UNEQ.

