## **Primary and Secondary Outcome Measures**

The initial primary outcome measure was the percentage of patients with: (1) no UNE symptoms or (2) symptoms markedly improved – only minor symptoms persist at 12 months follow-up. However, due to the inclusion of only patients with moderate or severe UNE in the present trial, and follow-up of only 12 months, the trial outcomes were much worse than expected based on our previous study results. That study also included patients with mild UNE and had a much longer follow-up of 2-3 years. Only 8 patients (13%) in the CTE arms of the present trial reached the primary outcome. Patients also often reported inability to reliably compare their current hand symptoms with symptoms one year ago. Therefore, as the primary outcome, we reported a comparison of patients' responses to standard UNEQ at the baseline and at 12-month follow-up. This outcome measure was also recommended by the authors of a recent Cochrane review.

As explained, we deleted instrumental measurements of the FDI muscle CSA using US and ADM/FDI muscle strength using a dynamometer, due to duplication of clinical gradings without added value, and a large number of secondary outcomes.

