## Statistics

The large majority of numerical variables were distributed non-normally, and therefore, non-parametric descriptive statistics (i.e., median (25th–75th percentile)) and a non-parametric comparison test (Mann-Whitney U) were used.

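### The primary UNEQ comparison has a test but no between-arm estimate or confidence interval, and no baseline-adjusted version

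*Combined protocol and SAP*

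**What the plan says.** Under Primary and Secondary Outcome Measures the protocol states: "The primary outcome measure of the study will be the change in UNEQ score from baseline at inclusion of patients into the study" and at 12 months. UNEQ is the mean of nine items graded 1 to 5 (History and Clinical Neurologic Examination), so it moves in steps of one ninth.

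The Statistics section chooses the analysis of numerical variables by a Shapiro-Wilk test. If the data are non-normal, medians and quartiles are given and "a non-parametric comparison test (Mann-Whitney U) will be used". If they are normal, means and SDs are given with a two-sample t-test. A calculated difference appears only for categorical data: "A two-sample Z-test will be used to calculate the difference between the two proportions".

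The changes section under Statistics reports that the non-parametric route was taken: "The large majority of numerical variables were distributed non-normally". The changes section on outcomes describes the new primary result as a comparison of patients' "responses to standard UNEQ at the baseline and at 12-month follow-up", without naming the two treatment arms. Under Sample Size Calculation it adds that "we do not know the minimal clinically important difference for UNEQ".

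No section specifies a between-arm estimate for UNEQ, a confidence interval for any outcome, or adjustment for baseline UNEQ.

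**The concern.** A two-sample test with two per-arm summaries yields a p-value and two medians. It does not say how much better one arm did, or how precisely that is known. Here the gap is costly for three reasons.

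- No important difference is known for UNEQ, and the sample size was calculated for a different outcome. Readers have no target effect to hold the result against and must judge it from its size and uncertainty.
- The trial is small. A non-significant result could be read as no benefit when a moderate difference remains possible.
- Readers will be tempted to subtract the two reported medians. That is a noisier estimate than the one belonging to the Mann-Whitney test, and it has no interval.

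Baseline UNEQ is recorded for everyone. A plain change score fixes its coefficient at 1, which can waste precision.

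**Working it through.** The plan gives no effect size, SD or power for UNEQ, so there is no figure of its own to reproduce. SDs and the baseline to 12-month correlation r are assumptions throughout.

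**1. Number of patients.** The changes section says: "Only 8 patients (13%) in the CTE arms of the present trial reached the primary outcome". 8/59 = 13.6% (rounds to 14) and 8/65 = 12.3% (rounds to 12). 8/60 = 13.3%, 8/63 = 12.7% and 8/64 = 12.5% all fit 13%. So N = 60–64, about 31 per arm if balanced. The RCC number is not given.

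**2. Precision, closed form.** With n per arm and normal data, the 95% half-width for the Mann-Whitney/Hodges-Lehmann shift is 1.96 × √(2/n) × √(π/3) SDs of change. For n = 31: 1.96 × 0.254 × 1.023 = 0.51 SD. For n = 30 and 32 it is 0.52 and 0.50. The difference detectable with 80% power is (1.96 + 0.84) × 0.254 × 1.023 = 0.73 SD.

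**3. Precision, simulated.** There were 27 settings with 6,000 trials each: 31 per arm, 12-month SD 0.8, effect 0.6 SD, means 2.9 (baseline) and 2.7 (12 months, control). Errors were normal, skewed (chi-square, 4 df) or heavy-tailed (t, 3 df). The first two were rounded to ninths and clipped to 1–5; the t errors were not clipped. Half-widths in SDs of change:

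- near-normal 0.52–0.53
- skewed 0.45–0.52
- heavy-tailed 0.41–0.44

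If the SD of change is 0.6–1.0 points, the range is 0.41 × 0.6 = 0.25 to 0.53 × 1.0 = 0.53 points.

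**4. Subtracting medians.** Across the settings, the SD of the difference of arm medians was 1.07–1.35 times that of the Hodges-Lehmann shift.

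**5. Baseline adjustment.** Let k be the baseline SD divided by the 12-month SD. In a linear model, the CI width after adjustment relative to the change score is √[(1 − r²)/(1 + k² − 2kr)]. At k = 1 and r = 0.5: √(0.75/1.00) = 0.866, or 13% narrower. At k = 0.7 and r = 0.7: √(0.51/0.51) = 1, no gain. Simulated narrowing when the same rank method is applied to the adjusted score, at r = 0.3/0.5/0.7:

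| k | near-normal | skewed | heavy-tailed |
|---|---|---|---|
| 0.7 | 9/4/1% | 13/5/0% | 12/5/0% |
| 1.0 | 20/14/9% | 25/18/11% | 26/19/13% |
| 1.4 | 34/30/27% | 38/33/29% | 40/36/34% |

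The first row is plausible, because the baseline range was restricted: the authors explain the poor outcomes as "due to the inclusion of only patients with moderate or severe UNE in the present trial".

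Near-normal power (%) at r = 0.3/0.5/0.7, Mann-Whitney on change against the adjusted method, was 57.3/71.8/87.2 against 65.5/75.2/87.8 at k = 0.7. At k = 1 it was 46.5/59.5/80.8 against 65.2/74.2/88.1.

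**6. Are the intervals sound?** Simulated coverage of the unadjusted interval was about 94–96% (95–98% in a simpler run with change rounded to ninths). For the adjusted interval it was 93.7–95.7% in the main runs and about 93–96% in a repeat. The adjusted test rejected a true null in 4.5–5.9% of trials. It lost power against Mann-Whitney in 1 of 27 settings (by 0.1 points). Linear ANCOVA lost in 9 (up to 12.2 points) and rank ANCOVA in 7 (up to 5.1). With arms of 26 and 36 the adjusted method lost in 1 (0.3 points), and with a strong floor at the bottom of the scale in none.

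**The case against.** Nobody need dispute that the estimate and interval are absent. The case against concerns the rest.

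- **Branch.** The changes section says most numerical variables were non-normal, not that UNEQ change was. It nevertheless reports Mann-Whitney as the test used. What stands: if UNEQ change was in fact analysed by t-test, the matching estimate is the mean difference with its 95% CI.
- **Contrast.** The parallel design and the two-sample tests already imply a between-arm comparison. That is fair; naming the contrast is a clarification.
- **Adjustment is a preference.** It improves efficiency and does not repair an invalid test, and with a narrow baseline spread it gains little. This stands, which is why the adjusted analysis is only supportive. The 27–40% gains need k = 1.4, which nothing in the documents supports.
- **Method.** The adjusted procedure treats an estimated slope as known and is slightly inexact, as the coverage and null rejection figures show. Under normal errors linear ANCOVA was better by 0.4–1.7 power points.
- **Heavy tails.** The unclipped t settings allow impossible scores. They produce the 0.41 SD lower end and inflate the case against linear ANCOVA: its worst loss, 12.5 points in a repeat run, fell to 5.0 after clipping. Losses of about 6–7 points remained in two skewed settings.
- **Analysis set.** Validity under randomisation presupposes an as-randomised analysis, which the plan does not state. That is a separate matter and does not close this gap.

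**Conclusion.** The concern holds. The plan tests the primary outcome without specifying how large the between-arm difference is or how precisely it is estimated. The planned test is not invalid, so this is a change that should be made and not a fatal flaw.

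In CTE, the missing interval would extend roughly half an SD of change either side of the estimate. That rests on about 31 per arm, inferred from one percentage, and the conversion to UNEQ points rests on an assumed SD of 0.6–1.0. The same cannot be sized for RCC. The case for the estimate and interval does not depend on these assumptions. The benefit of baseline adjustment does: it runs from nothing to about 40% in CI width, and the lower part of that range is plausible here.

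**What to change.** Two sentences in the Statistics section would do it.

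1. State that the primary contrast is surgery minus conservative in UNEQ change, separately within CTE and within RCC because these were randomised separately. Report the planned Mann-Whitney test together with the Hodges-Lehmann shift in UNEQ points and its 95% CI. Explain that the shift is the median of all pairwise between-arm differences and not the difference of the two medians, and say that it was added after outcomes were seen.
2. Add one supportive analysis, labelled post hoc: apply the same procedure to 12-month UNEQ minus b × baseline UNEQ, where b is the common within-arm slope. Report the adjusted shift, 95% CI and p-value, and state how b was fitted.

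Nothing further is asked for the secondary outcomes.

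The cost is small. No new patients or data are needed, and the point estimate is the median of about 31 × 31 = 961 differences, which the planned spreadsheet can hold. The interval and b need a little more calculation. The downsides are these: the interval will be wide; the shift reads as a simple location difference only if the arms have similar shapes; and the adjusted result may differ from the planned test, cannot replace it, and may add almost nothing if baseline scores are tightly grouped. The planned test's own power does not change.

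### Severity, atrophy and sensation grades are not assigned to a test, and both tests open to them use the data less efficiently than a full-scale, baseline-adjusted analysis

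*Combined protocol and SAP*

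**What the plan says.** The Statistics section sets two routes. Numerical variables go to a t-test or a Mann-Whitney U test, depending on a Shapiro-Wilk test. For the rest, "Categorical variables will be presented as frequencies and percentages", followed by "A two-sample Z-test will be used to calculate the difference between the two proportions". No cut-point, ordinal method or baseline adjustment is given. The significance level is 0.05, two-sided.

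Under Changes to the protocol, the Statistics entry reports that most numerical variables were non-normal, so that "a non-parametric comparison test (Mann-Whitney U) were used".

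The History and Clinical Neurologic Examination section defines the grades. Sensation is scored "0 – normal, 1 – moderately reduced, 2 – severely reduced or 3 – absent", atrophy also runs from 0 to 3, and clinical severity has three levels. Only the MRC strength scale is explicitly recoded for analysis, to 0-7. The Primary and Secondary Outcome Measures section lists all four as secondary outcomes (items 1 to 4 of nine), each defined as a change.

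**The concern.** The text does not settle which route severity, atrophy and sensation take.

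- **As categorical variables**, they fall to a two-proportion Z-test. A three- or four-level grade must then be reduced to yes/no, and the analyst chooses the cut with the data in hand.
- **As numerical variables**, they fall to Mann-Whitney on the change in grade. A fall from 3 to 2 then ties with a fall from 1 to 0, and a patient who starts at 0 is unchanged at best because no improvement is possible.

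Neither route uses the baseline grade as a covariate, although every patient has one. At stake is the chance of detecting a real difference in clinical recovery in a small trial, together with an avoidable freedom in choosing the test and the cut.

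**Working it through.** **The plan's own figure.** No final sample size or power is stated. The only usable count, under Changes to the protocol, is "Only 8 patients (13%) in the CTE arms of the present trial reached the primary outcome". 8/60 = 13.3% and 8/63 = 12.7%, so a total of 60 to 63 rounds to 13%. With "parallel trial design with a 1:1 allocation ratio" this is about 31 per CTE arm. That is an assumption: allocation is by dice, and arm sizes are not given. No RCC count is given.

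**Simulation of the graded outcomes.**

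*Inputs (assumed unless noted):* 31 per arm; four grades (documents: atrophy and sensation 0-3) of equal baseline frequency before any restriction; latent bivariate normal severity with baseline-to-12-month correlation rho = 0.6; benefit of 0.6 SD in one arm; two-sided 0.05 (documents).

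*Methods compared:*
1. Z-test on improved/not improved: z = (p1 − p2) / √[p(1 − p)(1/n1 + 1/n2)], with p the pooled proportion.
2. Mann-Whitney on d = 12-month grade − baseline grade.
3. Rank ANCOVA: rank the baseline grades and the 12-month grades over both arms, regress the second ranks on the first, and compare the residuals between arms.

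| Baseline | Z on improved | Mann-Whitney on change | Rank ANCOVA |
|---|---|---|---|
| Grades 0-3 allowed | 39% | 55% | 69% |
| Grade 0 excluded | 63% | 68% | 74% |

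Type I error was near 5% for all three methods. The first row fits atrophy, since entry requires sensory loss and weakness but not atrophy. The second fits fifth-finger sensation, where loss is an entry criterion. With grade 0 allowed, rho = 0.5 gave 35/49/64% and rho = 0.7 gave 46/62/75%, in the same order.

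The gain of rank ANCOVA over Mann-Whitney is 69 − 55 = 14 points with grade 0 allowed and 74 − 68 = 6 points without it. Over the Z-test it is 69 − 39 = 30 and 74 − 63 = 11 points.

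**Cost of a cut on a three-level grade, by a different model.** This used 31 per arm and an assumed proportional odds ratio of 3.5, with outcome grades only and no baseline. With control grades in equal thirds, Mann-Whitney on the full scale had 73% power; the Z-test had 70% at one cut and 51% at the other. With control grades split 10/60/30%, the figures were 67% against 45% and 47%. The loss depends heavily on the cut, which the plan does not state.

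**Is the Z-test itself sound when events are few?** Full binomial enumeration at 31 v 31 and a 13% rate gives the pooled Z-test a true size of 5.5%. For an illustrative 7 v 1 split of the 8 events: p1 − p2 = 7/31 − 1/31 = 0.1935; p = 8/62 = 0.129; standard error = √(0.129 × 0.871 × 2/31) = 0.0852; z = 2.27; p-value 0.023. Boschloo's and Barnard's tests both give 0.030 and Fisher's 0.053. Fisher's true size here is only 1.5%, so its different answer reflects its conservatism.

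**The case against.** The strongest reply is that nothing is wrong, only unspoken. The grades carry number codes, the outcomes are changes in them, and Mann-Whitney is reported as used for non-normal numerical variables, so a rank test on the grades is a natural reading. It holds its size. Preferring rank ANCOVA is then an efficiency choice for secondary outcomes, made after results are known. The population also narrows the gain: all patients had sensory loss and weakness at entry, so severity cannot start at its lowest level and fifth-finger sensation should rarely start at 0.

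Much of this stands. A reader might infer that the plan dichotomises the grades. It does not say so, and the Z-test figures apply only if that route is taken. The row with grade 0 allowed is near the unfavourable end and fits atrophy best. The gain over Mann-Whitney may be only about 6 points for sensation.

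A reader might also infer that the Z-test gives unreliable p-values because events are few. The documents and the arithmetic do not support that. The pooled test's size is close to nominal, and two exact tests agree with it at 7 v 1. The 8 events belong to an outcome since replaced as primary, with no split by arm, and no listed secondary outcome is defined as yes/no. There is no case here for replacing the Z-test with an exact test.

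What the objection does not answer is that the assignment is left open, no cut is given, and no route uses the baseline grade as a covariate.

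**Conclusion.** The point holds as one of specification and efficiency. The plan does not assign severity, atrophy and sensation to a test, and both available routes have lower power than a full-scale analysis adjusted for baseline: about 39-63% and 55-68% against 69-74%.

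These figures rest on assumed values for arm size, correlation, effect and grade distribution; none is trial data. The order of the methods was stable over the correlations tried, but the size of the gain was not. The main simulation used four grades, so its figures carry over to three-level severity in direction only. Strength already has a numerical route and shares only the lack of baseline adjustment. No bias or inflated type I error is shown, and the primary UNEQ comparison is untouched. It is a worthwhile, inexpensive improvement to secondary analyses.

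**What to change.** In the Statistics section, state that severity, atrophy, sensation and the recoded MRC strength score are compared between arms at 12 months on their full ordered scale by rank ANCOVA, with the baseline grade as covariate and without dichotomising. Report beside each the numbers improved, unchanged and worsened per arm.

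Because outcome data have already been seen, label this analysis post hoc, say which test was originally applied to each grade (with the cut, if there was one), and keep that result beside the new one.

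The cost is a few sentences and a short re-analysis of existing data, probably in a general statistics package rather than the web calculator. The downside is the post hoc label, which limits the weight a newly significant result can carry.
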